## 5.1 Follow-up for Patients

The follow-up requirements for ineligible randomized patients who have received no protocol therapy include submission of the Baseline Report and an End of Treatment Report. Data submission for ineligible participants who have received at least one dose of protocol therapy should be according to the protocol to allow for treatment and adverse event assessment. For patients without detectable POLE or POLD1 mutations on cfDNA screening, no follow-up is required.

## 6.0 ENTRY/RANDOMIZATION PROCEDURES

### 6.1 Entry Procedures

All registrations and randomizations will be done through the CCTG web-based, password-operated Electronic Data Capture (EDC) system. Complete details regarding obtaining a password, accessing the system and registering/randomizing patients will be provided at the time of study activation and will also be included in the “EDC Data Management Guidebook”, posted on the CRI-CCTG-0001 trial specific web-site. If sites experience difficulties accessing the system and/or registering/randomizing patients, please contact the help desk (link in EDC) or the CRI-CCTG-0001 Study Coordinator.

All patients who are registered by the participating treatment center will be assigned a serial number which must be used on all documentation and correspondence with CCTG.

#### Registration for Screening

All consenting patients who are believed to be eligible will be registered prior to the collection and submission of a cfDNA screening sample for POLE/POLD1. The completion of an abbreviated eligibility check will be required and a serial number assigned which must be used to identify the patient on the samples sent for testing. Details of the central laboratory including sample collection and shipment are provided in the CRI-CCTG-0001 Screening Manual.

The following information will be required for screening and enrollment:

- trial code (CRI-CCTG-0001)
- patient's initials (may be coded)
- screening informed consent version date, date signed by patient, name of person conducting consent discussion and date signed
- confirmation of the requirements listed in Section 4.0

#### Randomization

Following receipt of the screening results, eligible patients will be randomized to one of two study arms.

The following additional information will be required:

- informed consent version date, date signed by patient, name of person conducting consent discussion and date signed
- tissue banking/optional consent version date
- confirmation of the requirements listed in Section 4.0, including dates of essential tests and actual laboratory values
- height and weight
- stratification factors

6.2 Stratification

Subjects will be stratified at the time of randomization by:

- ECOG performance status (0, 1)
- Number of prior treatments (0, 1-2, 3 or more)

6.3 Registration and Randomization

Registration and Randomization will be provided electronically.

Note: The validity of results of the trial depends on the authenticity of and the follow-up of all patients entered into the trial. Under no circumstances, therefore, may an allocated patient's data be withdrawn prior to final analysis, unless the participant withdraws from the trial and requests that data collection/submission cease from the point in time of withdrawal.

All eligible patients admitted to the trial will be followed by the coordinating center. It is the responsibility of the physician in charge to satisfy himself or herself that the patient is indeed eligible before requesting registration.

All randomized patients are to be followed until death or until sites are informed by CCTG that further follow-up is no longer required. The follow-up requirements for ineligible patients are outlined in Section 5.1.

## 7.0 TREATMENT PLAN

Although the Canadian Cancer Trials Group acts as the coordinating agency for the trial, the responsibility for treatment of patients rests with the individual investigator.

In accordance with CCTG policy, protocol treatment is to begin within 2 working days of patient randomization.

### 7.1 Treatment Plan

#### 7.1.1 Drug Administration

When nivolumab is given with ipilimumab, nivolumab will be administered first. Prior to the ipilimumab infusion, the patient's line should be flushed and filter changed. The ipilimumab infusion should not be started until 30 minutes after the end of the nivolumab infusion.

One cycle will be defined as 6 weeks.

Arm	Agent(s)	Dose	Route	Duration	Schedule
1 & 2	Nivolumab	240 mg	IV	30 min	Day 1, then every 2 weeks
2	Ipilimumab	1 mg/kg	IV	30 min	Day 1, then every 6 weeks

#### 7.1.2 Premedication

Premedication (e.g. for nausea) or hypersensitivity prophylaxis is not required. Management of symptoms should take place as necessary (see Section 7.1.6 below). Details of any premedication or concomitant medication given to manage or prevent adverse events should be recorded on the electronic case report form (eCRF).

#### 7.1.3 Patient Monitoring

Vital signs should be taken as per institutional standard of care prior to, during and after drug administration.

All patients should be closely monitored according to guidelines in Section 5.0 and be advised to contact the treating center in the case of significant toxicities.

#### 7.1.4 Dose Modifications

The major toxic effects of nivolumab or ipilimumab which are anticipated to limit dosing are hypersensitivity/ infusion related reactions and possible class related immune related AEs, based on the mechanism of action of nivolumab and ipilimumab leading to T-cell activation and proliferation. Potential immune related AEs include pneumonitis, enterocolitis, dermatitis, hepatitis/hepatotoxicity, neuropathy/neuromuscular toxicity, pancreatitis, nephritis and endocrinopathy. Patients should be monitored for signs and symptoms of immune related AEs. In the absence of an alternate etiology (e.g. infection or relapse), signs or symptoms of pneumonitis, enterocolitis, dermatitis, hepatitis/hepatotoxicity, neuropathy/neuromuscular toxicity, pancreatitis, nephritis and endocrinopathy should be considered to be immune-related.

The guidelines which follow outline dose adjustments for several of these toxic effects. If a patient experiences several adverse events and there are conflicting recommendations, please use the recommended dose adjustment that requires the greatest dose hold or discontinuation. Adverse events will be graded using the NCI Common Terminology Criteria for Adverse Events (CTCAE) (see Appendix V).

Dose adjustments (slowing/interruption of infusion rate, omission of a dose, or permanent discontinuation) will be made for adverse events. There will be no dose reductions.

If the infusion cannot be administered, it should be omitted until the next planned infusion. When nivolumab is administered in combination with ipilimumab, if either agent is withheld, the other agent should also be withheld. If dosing is resumed after a delay either the combination treatment or nivolumab alone can be resumed based on evaluation of the individual patient.

Treatment should not be given (including day 1 cycle 1) until the laboratory criteria in Section 4.2.3 are met and resolution of all drug related toxicity to  $\leq$  grade 2. Discuss with CCTG if asymptomatic/not felt to be clinically significant.

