#### 7.1.4.1 *Dose Delays*

Dose delay criteria apply for all drug-related adverse events (regardless of whether or not the event is attributed to nivolumab, ipilimumab, or both). Refer to Appendix II for full details of toxicity management. Nivolumab and ipilimumab administration should be delayed for the following:

- Any Grade  $\geq$  2 non-skin, drug-related adverse event, with the following exceptions:
  - Grade 2 drug-related fatigue or laboratory abnormalities do not require a treatment delay.
- Any Grade 3 skin, drug-related adverse event
- Any Grade 3 drug-related laboratory abnormality, with the following exceptions for AST, ALT, or total bilirubin:
  - If a patient has a baseline AST, ALT, or total bilirubin that is within normal limits, delay dosing for drug-related Grade  $\geq$  2 toxicity.
- Any adverse event, laboratory abnormality, or intercurrent illness which, in the judgment of the investigator, warrants delaying the dose of study medication.

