#### 7.1.5 Management of Toxicity

See Appendix II for full details of toxicity management.

For adverse events (AEs) that are considered at least partly due to administration of nivolumab and/or ipilimumab the following dose adjustment guidance may be applied:

- Treat each of the toxicities with maximum supportive care (including holding the agents suspected of causing the toxicity where required).
- If the symptoms promptly resolve with supportive care, consideration should be given to continuing nivolumab or ipilimumab along with appropriate continuing supportive care. If medically appropriate, dose delays are permitted for nivolumab and/or ipilimumab (see Appendix II).
- All dose delays should be documented with clear reasoning and documentation of the approach taken.
- In addition, there are certain circumstances in which nivolumab or ipilimumab should be permanently discontinued.

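### For non-skin, non-laboratory grade 2 events, the dosing threshold in 7.1.4 is already met while 7.1.4.1 still requires a hold, and no general resume grade is stated in the readable text

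*Combined protocol and SAP*

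**What the plan says.** All references are to the combined protocol and SAP.

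Section 7.1.4 (Dose Modifications) sets a general bar. Treatment is not to be given "until the laboratory criteria in Section 4.2.3 are met and resolution of all drug related toxicity to" grade 2 or lower. The bar also covers day 1 of cycle 1, and sites are to talk to CCTG when a finding is asymptomatic or not thought clinically significant.

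Section 7.1.4.1 (Dose Delays) lists when both drugs must be held. The first trigger is any grade 2 or higher "non-skin, drug-related adverse event, with the following exceptions": "Grade 2 drug-related fatigue or laboratory abnormalities do not require a treatment delay". Skin events trigger a delay at grade 3. Laboratory abnormalities do so at grade 3, with a separate rule for liver tests: "If a patient has a baseline AST, ALT, or total bilirubin that is within normal limits, delay dosing for drug-related Grade" 2 or higher. The section also says: "Refer to Appendix II for full details of toxicity management".

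On restarting, 7.1.4 says: "If dosing is resumed after a delay either the combination treatment or nivolumab alone can be resumed based on evaluation of the individual patient". Section 7.1.5 (Management of Toxicity) says: "If the symptoms promptly resolve with supportive care, consideration should be given to continuing nivolumab or ipilimumab along with appropriate continuing supportive care".

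**The concern.** A hold rule needs a trigger and a release. Section 7.1.4.1 supplies the trigger but no release grade. The only general toxicity threshold for giving treatment in the readable text is the grade 2 ceiling in 7.1.4. For an event held at grade 2, that ceiling is satisfied on the day the hold begins, so it gives the site no guidance on when the hold ends.

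What is at stake is patient safety. Section 7.1.4 itself warns of immune-mediated harm: "Potential immune related AEs include pneumonitis, enterocolitis, dermatitis, hepatitis/hepatotoxicity, neuropathy/neuromuscular toxicity, pancreatitis, nephritis and endocrinopathy". A site that treats the 7.1.4 sentence as its release rule could give nivolumab, with or without ipilimumab, while a grade 2 event of this kind persists. Sites could also differ in when they restart.

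**Working it through.** There is no planned figure to reproduce. The check sets the two rules side by side, grade by grade.

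**Inputs.** The toxicity ceiling is grade 2 (7.1.4). The laboratory limits that must also be met include AST and/or ALT at most 3 x ULN and bilirubin at most 1.5 x ULN, or 3 x ULN in confirmed Gilbert's (4.2.3). The triggers are the four grade-based ones in 7.1.4.1; a fifth, investigator judgement, carries no grade.

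**Step 1. Lowest grade that starts a hold, against the ceiling.**

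| 7.1.4.1 trigger | Hold starts at | 7.1.4 condition at that grade | Result |
|---|---|---|---|
| Non-skin, non-laboratory drug-related event (grade 2 fatigue excepted) | 2 | 2 ≤ 2, met | Mismatch |
| Skin event | 3 | 3 > 2, not met | Consistent |
| Laboratory abnormality in general | 3 | 3 > 2, not met | Consistent |
| AST, ALT or bilirubin, normal at baseline | 2 | Grade part met, but the 4.2.3 limits apply as well | Not counted |

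The mismatch is therefore shown for 1 of 4 grade-based triggers. Grade 2 fatigue and exempt grade 2 laboratory abnormalities start no hold and raise no problem.

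**Step 2. Events that start at grade 3 and improve.** When a non-skin, non-laboratory grade 3 event falls to grade 2, the ceiling is met while the delay trigger is still present. Section 7.1.4.2 narrows this. It requires permanent discontinuation for grade 3 uveitis, pneumonitis, bronchospasm, diarrhea, colitis, neurologic toxicity, hypersensitivity and infusion reactions of any duration, and for other grade 3 non-skin, non-laboratory events lasting more than 7 days. Only events outside that list that leave grade 3 within 7 days remain. Fatigue drops out too, because it is exempt at grade 2.

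**Step 3. Search for another general restart grade.**

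- The 7.1.4 sentence on resuming says which drugs may restart, not at what grade.
- The 7.1.4 rule to follow the greatest hold is worded for a patient with several events and conflicting advice, not for one event under two rules.
- The CCTG discussion clause in 7.1.4 adds discretion, not a grade.
- Section 7.1.5 links continuing to prompt resolution of symptoms. It is permissive and gives no grade.
- Section 7.1.4.2 requires CCTG consultation before a restart only after interruptions longer than 6 weeks. It names recovery to grade 1 only for grade 2 eye events, as part of a discontinuation rule.

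None of these supplies a general restart grade.

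**Step 4. Grades used elsewhere.** Section 4.2.2 requires recovery to grade 1 or lower from earlier systemic or radiation toxicity before enrollment. With the eye-event rule, this makes grade 1 a benchmark that the protocol already uses.

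**The case against.** The strongest reply is that the two rules do not contradict each other. The 7.1.4 sentence states a necessary condition; it does not authorise dosing once grade 2 is reached. A missed infusion is skipped until the next planned one. If the event is still grade 2 then, the 7.1.4.1 trigger is still present and the dose is held again. Both rules are satisfied at grade 1 or lower, and the grade 2 ceiling still does work for skin events, fatigue and exempt laboratory abnormalities. A general floor with a stricter specific rule is ordinary drafting.

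Most of this stands. A reader might infer that the protocol permits re-dosing at grade 2, or that it is flatly self-contradictory. The text supports neither. What remains is that the joint reading is left to inference: a site must derive the restart grade from a hold trigger, and the only stated ceiling has no effect for the events in question.

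A reader might also count the liver-test trigger and report 2 of 4. That is not supported. The same 7.1.4 sentence requires the 4.2.3 limits, which give AST, ALT and bilirubin a numeric condition of their own. Whether a grade 2 value would also pass those limits depends on CTCAE version 5.0 cut-offs, which the document does not reproduce.

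Finally, 7.1.4.1 and 7.1.5 both point to Appendix II. Its flowcharts cannot be read here, but a surviving hepatic footnote on delaying rather than discontinuing shows that they carry dosing rules. A reader might infer that no restart grade exists anywhere in the plan; that cannot be claimed. Nor do the headings settle coverage. There are headings for seven of the eight immune-related classes named in 7.1.4, all but pancreatitis. However, the appendix title omits renal although a renal algorithm is present, so labels do not define content. It does stand that 7.1.4.1 covers all drug-related events, and any event outside the algorithms depends on the general text.

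**Conclusion.** The point holds as a mismatch in a dosing-safety rule, confined to non-skin, non-laboratory drug-related events at grade 2 other than fatigue. It extends to grade 3 events that fall to grade 2 only where 7.1.4.2 does not require permanent discontinuation. It affects 1 of the 4 grade-based triggers. No event frequencies are given, so the number of patients affected cannot be computed.

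Severity is low to moderate. The stricter joint reading is probably intended, 7.1.5 leans towards waiting for symptoms to resolve, and Appendix II may settle the matter for the organ systems it covers. The conclusion rests on the readable text alone and concerns only the absence of a stated general restart grade. A reader might infer that the trial's results are affected; they are not in question, because the definition of objective response, the sample size and the error rates do not depend on this rule.

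**What to change.** Amend the toxicity sentence in 7.1.4 so that it refers to 7.1.4.1. Suggested sense: *dosing resumes only when the 4.2.3 laboratory criteria are met and no delay criterion in 7.1.4.1 is still present, that is, drug-related toxicity is at grade 1 or lower, or at baseline.* List the exceptions in the same place: grade 2 skin events, grade 2 fatigue, grade 2 laboratory abnormalities that 7.1.4.1 exempts, and any event for which Appendix II allows resumption at grade 2. Check the wording against the Appendix II flowcharts before issue, so that the general rule and the algorithms agree.

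The cost is a wording amendment and a notice to sites. The downside is possibly a few more held doses, at sites that would otherwise have restarted at grade 2.

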#### 7.1.4.1 *Dose Delays*

Dose delay criteria apply for all drug-related adverse events (regardless of whether or not the event is attributed to nivolumab, ipilimumab, or both). Refer to Appendix II for full details of toxicity management. Nivolumab and ipilimumab administration should be delayed for the following:

- Any Grade  $\geq$  2 non-skin, drug-related adverse event, with the following exceptions:
  - Grade 2 drug-related fatigue or laboratory abnormalities do not require a treatment delay.
- Any Grade 3 skin, drug-related adverse event
- Any Grade 3 drug-related laboratory abnormality, with the following exceptions for AST, ALT, or total bilirubin:
  - If a patient has a baseline AST, ALT, or total bilirubin that is within normal limits, delay dosing for drug-related Grade  $\geq$  2 toxicity.
- Any adverse event, laboratory abnormality, or intercurrent illness which, in the judgment of the investigator, warrants delaying the dose of study medication.

#### 7.1.4.2 *Discontinuation (Unacceptable Toxicity)*

Treatment should be permanently discontinued for the following:

- Any Grade 2 drug-related uveitis or eye pain or blurred vision that does not respond to topical therapy and does not improve to Grade 1 severity within the re-treatment period OR requires systemic treatment.
- Any Grade 3 non-skin, drug-related adverse event lasting  $>$  7 days, with the following exceptions for drug-related laboratory abnormalities, uveitis, pneumonitis, bronchospasm, diarrhea, colitis, neurologic toxicity, hypersensitivity reactions, and infusion reactions:
  - Grade 3 drug-related uveitis, pneumonitis, bronchospasm, diarrhea, colitis, neurologic toxicity, hypersensitivity reaction, or infusion reaction of any duration requires discontinuation

- Grade 3 drug-related laboratory abnormalities do not require treatment discontinuation except:
  - Grade 3 drug-related thrombocytopenia > 7 days or associated with bleeding requires discontinuation
  - Any drug-related liver function test (LFT) abnormality that meets the following criteria require discontinuation:
    - AST or ALT > 8 x ULN
    - Total bilirubin > 5 x ULN
    - Concurrent AST or ALT > 3 x ULN and total bilirubin > 2 x ULN
- Any Grade 4 drug-related adverse event or laboratory abnormality, except for the following events which do not require discontinuation:
  - Isolated Grade 4 amylase or lipase abnormalities that are not associated with symptoms or clinical manifestations of pancreatitis and decrease to < Grade 4 within 1 week of onset.
  - Isolated Grade 4 electrolyte imbalances/abnormalities that are not associated with clinical sequelae and are improved with supplementation/appropriate management within 72 hours of their onset.
- Any dosing interruption lasting > 6 weeks with the following exceptions:
  - Dosing interruptions to allow for prolonged steroid tapers to manage drug-related adverse events are allowed. Prior to re-initiating treatment in a patient with a dosing interruption lasting > 6 weeks, the CCTG must be consulted. Tumor assessments should continue as per protocol even if dosing is interrupted.
  - Dosing interruptions > 6 weeks that occur for non-drug-related reasons may be allowed if approved by CCTG. Prior to re-initiating treatment in a patient with a dosing interruption lasting > 6 weeks, CCTG must be consulted. Tumor assessments should continue as per protocol even if dosing is interrupted.
- Any adverse event, laboratory abnormality, or intercurrent illness which, in the judgment of the investigator, presents a substantial clinical risk to the patient with continued nivolumab or ipilimumab dosing.

The assessment for discontinuation of nivolumab should be made separately from the assessment made for discontinuation of ipilimumab. Although there is overlap among the discontinuation criteria, if discontinuation criteria are met for ipilimumab but not for nivolumab, treatment with nivolumab may continue if ipilimumab is discontinued.

If a participant in the nivolumab/ipilimumab combination arm meets criteria for discontinuation and investigator is unable to determine whether the event is related to both or one study drug, the participant should discontinue both nivolumab and ipilimumab and be taken off the treatment phase of the trial.

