## Hepatic Adverse Event Management Algorithm

Rule out non-inflammatory causes. If non-inflammatory cause, treat accordingly and continue I-O therapy. Consider imaging for obstruction.

[figure not shown]
Patients on IV steroids may be switched to an equivalent dose of oral corticosteroids (e.g. prednisone) at start of tapering or earlier, once sustained clinical improvement is observed. Lower bioavailability of oral corticosteroids should be taken into account when switching to the equivalent dose of oral corticosteroids.

\*I-O therapy may be delayed rather than discontinued if AST/ALT ≤ 8 x ULN and T.bili ≤ 5 x ULN.

\*\*The recommended starting dose for grade 4 hepatitis is 2 mg/kg/day methylprednisolone IV.

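### The Appendix II hepatic footnote, as printed, permits delay at AST/ALT >3–8x with bilirubin >2–5x ULN, where Section 7.1.4.2 requires permanent discontinuation

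*Combined protocol and SAP*

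**What the plan says.** Section 7.1.4.2 requires permanent discontinuation for a liver-test abnormality attributed to study drug if any one of three criteria is met: AST or ALT above 8x ULN, total bilirubin above 5x ULN, or "Concurrent AST or ALT > 3 x ULN and total bilirubin > 2 x ULN".

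The Appendix II hepatic algorithm carries the footnote "I-O therapy may be delayed rather than discontinued if AST/ALT ≤ 8 x ULN and T.bili ≤ 5 x ULN". The flowchart to which its asterisk belongs is not reproduced in the available text.

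Sections 7.1.4.1 and 7.1.5 both refer sites to Appendix II for how toxicity is to be managed. Section 7.1.5 then adds: "In addition, there are certain circumstances in which nivolumab or ipilimumab should be permanently discontinued".

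Section 7.1.4 has a tie-break in favour of the stricter action. Its condition is "If a patient experiences several adverse events and there are conflicting recommendations". Section 10.1 defines unacceptable toxicity by reference to Section 7.0.

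On restarting, Section 7.1.4 says: "If dosing is resumed after a delay either the combination treatment or nivolumab alone can be resumed based on evaluation of the individual patient". For long interruptions, Section 7.1.4.2 says: "Prior to re-initiating treatment in a patient with a dosing interruption lasting > 6 weeks, the CCTG must be consulted".

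**The concern.** The same liver event can fall under a mandatory permanent stop in the protocol body and a permitted delay in the appendix that sites are told to consult. The omitted criterion is the combined one, in which transaminases and bilirubin are raised together.

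What is at stake is rechallenge after recovery. Dosing during the event is already restrained, because Section 7.1.4 says "Treatment should not be given (including day 1 cycle 1) until the laboratory criteria in Section 4.2.3 are met", subject to discussion with the coordinating group when the finding is asymptomatic or not thought clinically significant. Once values recover, the two texts lead to different places.

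- **Under 7.1.4.2**, the drug responsible is stopped for good. In Arm 1 that is nivolumab. In Arm 2 each drug is assessed separately: "if discontinuation criteria are met for ipilimumab but not for nivolumab, treatment with nivolumab may continue if ipilimumab is discontinued". If attribution between the two cannot be determined, both stop.
- **Under the footnote**, the event is a delay, and the Section 7.1.4 provision on resuming the combination or nivolumab alone applies. Consultation before restart is compulsory only when the interruption exceeds 6 weeks. A patient who recovers to the Section 4.2.3 limits sooner could be re-exposed to the causative drug without it.

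**Working it through.** The plan gives no figure to reproduce. The check compares two threshold rules.

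**Inputs.** Let A be AST or ALT and B total bilirubin, both in multiples of ULN, for a drug-related abnormality.

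- Stop rule (Section 7.1.4.2): A > 8, or B > 5, or (A > 3 and B > 2).
- Delay rule (Appendix II hepatic footnote as printed): A ≤ 8 and B ≤ 5.

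**Overlap.** The delay rule excludes the first two limbs of the stop rule, so only the third can coincide with it. Both rules therefore apply when 3 < A ≤ 8 and 2 < B ≤ 5.

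**Grid check.** On a grid with steps of 0.1 from 0 to 12 on both axes, both rules apply at 1,500 points. The rectangle holds 50 × 30 = 1,500 points, so every conflicting point lies inside it and none outside.

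**Spot checks.**

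| A | B | 7.1.4.2 stops? | Footnote allows delay? | Conflict |
|---|---|---|---|---|
| 3 | 2 | no | yes | no |
| 3.1 | 2.1 | yes | yes | yes |
| 5 | 3 | yes | yes | yes |
| 8 | 5 | yes | yes | yes |
| 8.1 | 1 | yes | no | no |
| 1 | 5.1 | yes | no | no |
| 5 | 1.5 | no | yes | no |

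The 8x and 5x limits agree exactly between the two texts. The only mismatch is the missing concurrent criterion.

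**Distance from the entry limits.** Section 4.2.3 admits AST/ALT up to 3x and bilirubin up to 1.5x ULN. A patient at both ceilings enters the conflict range with any further AST/ALT rise plus a bilirubin rise of more than (2.0 − 1.5)/1.5 = 33%. This needs both ceilings at once and a drug-related rise, so it shows only that the range is reachable, not how often it is reached.

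**Effect of the added clause.** The delay rule becomes A ≤ 8 and B ≤ 5 and not (A > 3 and B > 2). That is the exact complement of the stop rule, so the overlap is empty.

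**The case against.** The strongest objection is that the footnote qualifies a flowchart box that cannot be seen. Saying that therapy may be delayed instead of discontinued suggests that the box itself orders discontinuation, but its grade and wording are unknown. If it is limited by grade or states the concurrent criterion, the conflict shrinks or vanishes. This stands, and it limits the point to the footnote as printed.

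The second objection is that the texts can be followed together. Section 7.1.4.2 is mandatory and the footnote permissive, so a site that discontinues satisfies both. This also stands. It does not remove the defect, which is permission to delay where stopping is required.

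The third is that the protocol already points to 7.1.4.2. Section 10.1 defines unacceptable toxicity through Section 7.0, Section 7.1.5 adds permanent discontinuation to its advice on delays, and the 7.1.4 tie-break favours the stricter action. Section 7.1.4.2 does not itself defer to Appendix II, and it separately requires stopping when the investigator sees substantial clinical risk. The direction is clear, but none of these passages says that 7.1.4.2 prevails over the footnote. The tie-break is worded for several adverse events, not for two rules on one liver event. Raised transaminases and raised bilirubin could be counted as two events, but a site should not have to infer that for a liver stopping rule.

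A reader might infer that Appendix II overrides 7.1.4.2, or that patients who meet the stopping rule will be rechallenged. The documents support neither. Nothing gives the footnote priority, and rechallenge would require a site to set aside an explicit stopping rule.

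**Conclusion.** The plan is wrong as written on this point: an appendix footnote and a stopping rule in the protocol body are inconsistent. The severity is minor. The conflict covers exactly AST/ALT >3x to 8x ULN together with bilirubin >2x to 5x ULN. The consequence is possible rechallenge with the causative drug after recovery.

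The conclusion rests on the footnote as printed and assumes that the unseen flowchart box neither restricts it by grade nor states the concurrent criterion. The documents give no basis for estimating how many patients would fall in the range, so no case count is offered. The size of the range in threshold units should not be read as a share of patients.

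A reader might also infer that the trial's results are affected. They are not: objective response rate, sample size and error rates do not depend on this text.

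**What to change.** First check the hepatic flowchart. If it does not already state the concurrent criterion, add to the footnote: *and the concurrent AST/ALT >3x ULN with total bilirubin >2x ULN criterion in 7.1.4.2 is not met*.

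If a precedence sentence is wanted, limit it to this: the liver discontinuation criteria of 7.1.4.2 prevail over the hepatic footnote. A general rule that the stricter of Section 7.1.4 and Appendix II applies would reach the other organ algorithms, whose flowcharts are also not shown, and might mandate stopping that 7.1.4.2 does not require.

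The cost is one clause in a protocol amendment, plus one sentence if precedence is stated. No visits, tests or patients are added. Rechallenge is removed only where 7.1.4.2 already requires discontinuation.
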